9.9.3.2 Primary efficacy analysis

A similar analysis process as described above for the primary biomarker risk algorithm analysis will be used to compare the placebo- and active-treated non-Hispanic/Latino Caucasian subjects within the high-risk group (ie, using a similar CPH model with covariates of center, gender, and education and an additional covariate of age but using a factor of high-risk treatment group instead of biomarker risk assignment). If this test is significant at the 0.01 level, it can be concluded that active treatment has delayed the development of mild cognitive impairment due to AD.

An exact partial likelihood function will be constructed to fit the Cox proportional hazards (CPH) model to accommodate events with the same times to the event. The robust sandwich estimate for the covariance matrix from the CPH model will be used. The analysis of the primary efficacy comparison will be conducted using the FAS and a CPH model of MCI due to AD events with a factor for treatment and including center, gender, education, and age as covariates.

Parameter estimates, 2-sided 99% CIs, and appropriate p-values for the hazard ratios obtained from the CPH model will be computed to test the null hypothesis of equality of the hazard functions between the high-risk pioglitazone and high-risk placebo treatment groups.

Assessment of the proportional hazards assumption for treatment group will be assessed. Plots of Schoenfeld residuals obtained from the CPH models that fit the primary MCI-to-AD endpoint versus ordered time of events along with a smoothing spline will be used to evaluate the proportional hazards assumption for treatment group. Systematic departures from a horizontal line are indicative of meaningfully non-proportional hazards. Diagnostic checks will be presented in CSR Appendix 16.1.9.

9.9.3.3 Supportive Nonparametric Interval-Censoring Analyses

Alternative methods of analysis may be considered should some of the underlying model assumptions seem inappropriate (eg, non-proportional hazards). The reasons for any changes to the planned approach and methods will be fully documented.

Most survival analysis methods, including the CPH model, work best when the true event date is known for each and every event which occurs during a study (eg, right censoring). For complex events such as MCI due to AD, generally the true event date is unknown and is only detected at a subsequent visit (ie, interval censoring).

Primary high-risk placebo versus low-risk placebo biomarker analysis

As a sensitivity analysis to the above primary biomarker risk assignment analysis, a nonparametric analysis which accounts for interval censoring by using a weighted generalized log-rank test, stratified by gender, will be done using SAS PROC ICLIFETEST with the option WEIGHT=FINKELSTEIN (which corresponds to a proportional hazards assumption).

Primary high-risk pioglitazone versus placebo efficacy analysis

As above, alternative methods of analysis may be considered if some of the underlying CPH model assumptions are violated; and a similar nonparametric sensitivity analysis using SAS PROC ICLIFETEST will be done to account for interval censoring and its possible effect on the results of the primary efficacy analysis.

9.9.3.4 Supportive Log-rank Sensitivity Analyses

Primary high-risk placebo versus low-risk placebo biomarker analysis

As a sensitivity analysis to the above primary biomarker risk assignment analysis, a log-rank test, stratified by gender, will be done using SAS PROC LIFETEST.

Primary high-risk pioglitazone versus placebo efficacy analysis

A similar log-rank sensitivity analysis as described above for the primary biomarker risk assignment analysis will be used to compare the placebo- and active-treated non-Hispanic/Latino Caucasian subjects within the high-risk group (ie, stratified by gender, but using a factor of high-risk treatment group instead of biomarker risk assignment category).

9.9.3.5 Supportive PPS and subgroup analyses

If more than 5% of total subjects in the FAS high-risk, non-Hispanic/Latino Caucasian subjects have major protocol violations, the primary efficacy analysis will also be performed based on the PPS.

Similarly, if more than 5% of total subjects in the FAS placebo (both high-risk and low-risk), non-Hispanic/Latino Caucasian subjects have major protocol violations, the primary biomarker analysis will also be performed based on the PPS.

For the primary efficacy variable (for both the primary efficacy comparison and for the primary biomarker comparison), subgroup analyses by:

- age at randomization (<75, ≥75)
- gender (female, male)
- baseline diabetic status (non-diabetic: baseline HbA1c <6.5%, diabetic: baseline HbA1c ≥6.5%)
- race/ethnicity (Hispanic/Latino and/or non-Caucasian, all subjects)
- baseline NPI-Q Apathy/Indifference Score (no symptoms; mild, moderate, or severe symptoms)
- regulatory geographic region (North America: US; Europe: UK, Germany, Switzerland; Rest of World: Australia)
- geographic region based on language (English, German)
- baseline statin use (based on the Standardized Drug Groupings maintained by Uppsala Monitoring Centre, sponsors of the WHO Drug dictionaries)

and other variables, if necessary, will be performed. Analysis results for subgroups containing less than 20% of the total subjects in the primary efficacy analysis population should be interpreted especially cautiously. The treatment groups will be compared within each subgroup.

CCI

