 - Approximately 314 subjects in the low-risk group: All subjects stratified to the low-risk stratum will also be randomized to maintain the stratification blind, but all subjects in this stratum will receive placebo.

- Non-Caucasian subjects and Hispanic/Latino Caucasian subjects. Subjects will be allocated to risk strata using the same algorithm as for the non-Hispanic/Latino Caucasian subjects.

Since all subjects screened at the time of Amendment 5 will be allowed to randomize if they continue to meet all eligibility criteria, it is estimated that approximately 3,500 will be randomized with the following groups:

- Non-Hispanic/Latino Caucasian subjects. Estimated 3,330 subjects further divided into:
 - Approximately 2,940 subjects in the high-risk group (pioglitazone, n=1,470; placebo, n=1,470).
 - Approximately 394 subjects in the low-risk group: All subjects stratified to the low-risk stratum will also be randomized to maintain the stratification blind, but all subjects in this stratum will receive placebo.
- Non-Caucasian subjects and Hispanic/Latino Caucasian subjects. Subjects will be allocated to risk strata using the same algorithm as for the non-Hispanic/Latino Caucasian subjects (n=167).

Because the data used to develop the biomarker risk algorithm was collected in non-Hispanic/Latino Caucasian subjects only, biomarker qualification will be based upon non-Hispanic/Latino Caucasian subjects in the placebo arm of the high-risk stratum compared to data from non-Hispanic/Latino Caucasian subjects in the low-risk stratum. Likewise, the primary analyses to evaluate the effects of pioglitazone versus placebo will be within the non-Hispanic/Latino Caucasian high-risk sub-group. CCI

An interactive response system will be used for central randomization. Stratification status and treatment assignment of all study participants will be double-blind. The randomization will be stratified based on participation in the vMRI substudy (approximately 300 subjects).

For subjects who are not participating in the vMRI substudy, subjects in the high-risk stratum will be randomized to pioglitazone and placebo in a 1:1 ratio. Subjects in the low-risk stratum will be randomized only to placebo.

For subjects who are participating in the vMRI substudy, subjects in the high-risk stratum will be randomized to pioglitazone and placebo in a 5:4 ratio. Subjects in the low-risk stratum will be randomized only to placebo.

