9.2 Major Protocol Violations

All subjects with major protocol violations will be identified prior to unblinding, and will be listed by study center and subject number.

Subjects with the following major protocol violations will be excluded from the per-protocol set (PPS) defined in Section 9.3:

- Age outside of the range 65 to 83, inclusive, at the screening visit.
- CDR Global Score > 0 at Baseline.
- MMSE \leq 24 at the screening visit (after adjusting for education and age as described in Appendix G of the protocol).
- Subject does not have at least one memory test above -1.5 SD of the demographically corrected normative mean at Baseline.
- At Baseline, the subject has a current diagnosis or history of any type of cognitive impairment or dementia, or has a current diagnosis or history of neurological/psychiatric disorder or any other diagnosis that significantly affects cognitive performance (eg, mental retardation, organic mental disorder).
- At Baseline, the subject has a current diagnosis of significant psychiatric illness, per Diagnostic & Statistical Manual of Mental Disorders, 4th Edition - Text Revision (DSM-IV-TR) (or DSM-V when published) (including but not limited to major depressive disorder, anxiety disorders) and is in an acute phase/episode, or the subject has a current diagnosis or history of schizophrenia or bipolar disorder.
- The subject has a glycosylated hemoglobin (HbA1c) >8.0% at the time of baseline or requires treatment with insulin, triple oral antidiabetic therapy or a PPAR- γ agonist. The subject should be on a stable antidiabetic regimen for at least 3 months prior to enrollment.
- The subject has a history of drug abuse (defined as any illicit drug use) or a history of alcohol abuse/dependence within 2 years prior to the Screening Visit.

- Low study drug compliance (<80%).
- Double-blind study medication exposure less than 6 months ($[\text{last dose date} - \text{first dose date} + 1/30.5] < 6$).
- Subject switched treatment during study.
- Randomized treatment different from actual treatment received.
- Incorrect risk stratum assignment used for randomization.
- Subject unblinded prematurely.

The above list may be revised and any additional major protocol violations (eg, related to prohibited concomitant medications) will be identified by the study team prior to final study unblinding.

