9.3 Analysis Sets

The safety analysis set will include all subjects who were randomized and received at least 1 dose of double-blind study medication. In safety summaries, subjects will be analyzed according to the treatment they received. In the event that a subject receives more than one treatment, the actual treatment will be defined as the one which is used most frequently. If the two most common treatments are used with equal frequency, then the randomized treatment will be used as the actual treatment.

The full analysis set (FAS) will include all subjects who were randomized, received at least one dose of study drug, and had at least one valid post-baseline value for assessment of primary efficacy. In FAS efficacy summaries, subjects will be analyzed by the treatment to which they were randomized.

The per-protocol analysis set (PPS) will include all FAS subjects who had no major protocol violations. In PPS efficacy summaries, subjects will be analyzed by the treatment to which they were randomized.

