9.9.3.1 Primary biomarker risk assignment algorithm analysis

In order to test the first hypothesis, a test from a Cox proportional hazards survival model will be used to compare data from non-Hispanic/Latino Caucasian subjects in the (placebo-treated) low-risk group (ie, the combined placebo groups) with data from non-Hispanic/Latino Caucasian subjects in the placebo-treated subjects in the high-risk group. The event in this analysis will be an adjudicated event of MCI due to AD (see Section 9.9.4 below). If this test is significant at the 0.01 level, it can be concluded that the diagnostic prognostic test has differentiated between subjects at low and high risk of being diagnosed with MCI due to AD within 5 years of taking the test.

An exact partial likelihood function will be constructed to fit the Cox proportional hazards (CPH) model to accommodate events with the same times to the event. The robust sandwich estimate for the covariance matrix from the CPH model will be used. The analysis of the primary biomarker comparison will be conducted using the FAS and a CPH model of MCI due to AD events with a factor for biomarker risk assignment and including center, gender, and education as covariates. (Except as otherwise noted, education will be treated as a continuous variable and measured in years for purposes of statistical modeling.)

Parameter estimates, 2-sided 99% CIs, and appropriate p-values for the hazard ratios obtained from the CPH model will be computed to test the null hypothesis of equality of the hazard functions between high-risk placebo and low-risk placebo.

Assessment of the proportional hazards assumption for risk assignment category will be assessed. Plots of Schoenfeld residuals obtained from the CPH models that fit the primary MCI-to-AD endpoint versus ordered time of events along with a smoothing spline will be used to evaluate the proportional hazards assumption for risk assignment category. Systematic departures from a horizontal line are indicative of meaningfully non-proportional hazards. Diagnostic checks will be presented in CSR Appendix 16.1.9.

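### The supportive per-protocol biomarker analysis applies tablet-compliance and exposure exclusions that have no treatment meaning in a placebo-only comparison

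*SAP*

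**What the plan says.** The primary biomarker comparison is settled on the FAS. SAP 9.9.3.1 states: "The analysis of the primary biomarker comparison will be conducted using the FAS". A per-protocol repeat is planned in SAP 9.9.3.5: "if more than 5% of total subjects in the FAS placebo (both high-risk and low-risk), non-Hispanic/Latino Caucasian subjects have major protocol violations", then "the primary biomarker analysis will also be performed based on the PPS".

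The SAP has one per-protocol set. SAP 9.3 reads: "The per-protocol analysis set (PPS) will include all FAS subjects who had no major protocol violations". The violations are listed in SAP 9.2. Most concern eligibility, cognition at baseline, the treatment received, the risk stratum used at randomization, or premature unblinding. Two concern adherence: study drug compliance below 80%, and "Double-blind study medication exposure less than 6 months". No version of the list is specific to the biomarker question. It is still open to change, since SAP 9.2 adds "The above list may be revised and any additional major protocol violations" before final unblinding.

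Everyone in the biomarker comparison is on placebo. One side is the high-risk placebo arm. For the other, SAP 6.4 says "Subjects in the low-risk stratum will be randomized only to placebo".

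**The concern.** Adherence criteria belong in a per-protocol set when the question is what a drug does in people who take it. The biomarker comparison has no treatment contrast. It asks whether genotype and age predict conversion, and the number of placebo tablets swallowed, or the number of months they were taken, does not bear on that. Baseline cognition, correct stratum assignment and receipt of placebo do bear on it.

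Both criteria are also measured after baseline. If a subject begins to miss tablets because cognition is declining, a compliance exclusion removes that subject because of the process the test is meant to predict. At stake is a supportive analysis of a primary objective: it would lose valid events, most noticeably in the low-risk group where few are expected, and its event rates could be too low.

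**Working it through.** **Inputs** (SAP 8.0 and 6.4)
- 5-year conversion: 15% high-risk placebo, 4% low-risk placebo, exponential model.
- Dropout: 12% per year.
- Placebo subjects, non-Hispanic/Latino Caucasian: minimum 1,173 and 314; expected 1,470 and 394.
- Two-sided alpha 0.01; stated biomarker power 99%.

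**The plan's own figure.** A pooled two-proportion test of 15% against 4% with 1,173 and 314 subjects has power 99.99%; with 314 in each group it is 98.5%. The stated 99% reproduces. It refers to the FAS comparison, which this point leaves alone.

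**Expected events.** Hazards per year are λ = -ln(0.85)/5 = 0.03250 (high-risk) and -ln(0.96)/5 = 0.00816 (low-risk). The dropout hazard is δ = -ln(0.88) = 0.12783. The hazard ratio is 0.03250/0.00816 = 3.98.

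Events = n × λ/(λ+δ) × (1 - exp(-5(λ+δ))):
- High-risk: 1,470 × 0.1118 = 164.3
- Low-risk: 394 × 0.0296 = 11.7

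**Precision.** SE(log HR) = √(1/e_high + 1/e_low) = √(1/164.3 + 1/11.7) = 0.303. The low-risk term supplies 0.0857 of the total variance of 0.0918. If a share x of converters is excluded in both strata, the SE is multiplied by 1/√(1-x). The values of x are assumed, because the documents give none.

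| Converters excluded (assumed) | High-risk events | Low-risk events | SE of log HR |
|---|---|---|---|
| 0% | 164 | 11.7 | 0.303 |
| 10% | 148 | 10.5 | 0.319 |
| 20% | 131 | 9.3 | 0.339 |
| 30% | 115 | 8.2 | 0.362 |

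That is a 5-19% increase for 10-30%. At the minimum sample (131.1 and 9.3 events) the SE goes from 0.339 to 0.406 at 30%.

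**Event rates and hazard ratio.** Let q be the excluded share of converters in a stratum, and assume 10% of non-converters are excluded throughout. The high-risk rate becomes 0.15(1-q)/[0.15(1-q) + 0.85 × 0.9], and the low-risk rate is formed in the same way from 0.04 and 0.96. The hazard ratio is the ratio of ln(1 - rate).
- q = 10% in both strata: 15.0% and 4.0%, HR 3.98. Exclusion is unrelated to outcome, so nothing moves.
- q = 30% in both: 12.1% and 3.1%, HR 4.03. The rates fall; the HR hardly changes.
- q = 30% high-risk, 10% low-risk: 12.1% and 4.0%, HR 3.15.
- q = 10% high-risk, 30% low-risk: 15.0% and 3.1%, HR 5.10.

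**Would the analysis run?** At 12% annual dropout, 1 - 0.88^0.5 = 6.2% of subjects leave by month 6. That is close to the 5% trigger on its own, although the FAS requirement of a valid post-baseline value removes some of them first.

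**Which criterion matters.** Six months at 30.5 days is 183 days, the nominal day of the first post-baseline cognitive visit (SAP 9.1.3). SAP 9.15 requires two consecutive 6-month visits for a confirmed event, so a usual converter is followed to about month 12 and normally passes the exposure rule. The exceptions are direct dementia cases, which Protocol 6.2.4 sends to adjudication at once, and a single diagnosis at the last visit (SAP 9.9.4). The compliance rule has no such limit and can exclude a converter at any time.

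**The case against.** The strongest reply is that no conclusion depends on this table. The hypothesis is tested on the FAS, the other sensitivity analyses default to the FAS (SAP 9.9), and SAP 9.1.3 counts all adjudicated events in time-to-event analyses whatever the last dose date. The per-protocol repeat is supportive and conditional. All of this stands, and it keeps the point minor.

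A reader might infer that the per-protocol set will preferentially remove early decliners. The documents do not show that. SAP 9.8 averages compliance over the whole dosing period and scores missing tablet returns as 100%, so a subject who forgets to bring bottles back counts as compliant. Falling below 80% over 36 months takes about 0.20 × 36 = 7.2 months of missed tablets, so a lapse near onset after years of good compliance would usually not exclude. At month 12 it takes 2.4 months. Partners also help to monitor medication if needed. Selection on the outcome is possible, but its size is unknown.

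For exposure, it can be argued that short exposure is close to short observation: Protocol 7.5 specifies only 6-monthly telephone contact after study medication is stopped, with no cognitive battery. A minimum-observation rule could be defended for a prognostic test. That weakens the exposure half of the point, but it would be a rule about observation and the SAP does not frame it that way. None of these arguments gives tablet compliance a role in the comparison.

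Finally, the increase in SE follows directly from the assumed exclusion rates, and any per-protocol set loses some precision. That is correct, which is why the range is illustrative only.

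**Conclusion.** The point holds as a minor mismatch between an analysis set and its question. A post-baseline adherence filter designed for the drug comparison is carried into a placebo-only prognostic comparison. Compliance is the main problem; the exposure criterion removes few confirmed converters.

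The cost is in precision and possibly in the event rates shown: an SE of 0.303 rising to 0.319-0.362 if 10-30% of converters are excluded. This rests on the planned 15% and 4% rates, 12% annual dropout, 1,470 and 394 subjects followed for 5 years, and exclusion rates that are assumed. The starting value of 0.303 is for the full expected placebo population, before any eligibility exclusions.

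It would go too far to say that the biomarker hazard ratio is biased or that the biomarker conclusion is at risk. With similar exclusion in both strata the ratio barely moves. A material shift needs converters to be excluded at different rates by risk stratum, and nothing in the documents suggests that they would be. The primary FAS result is unaffected.

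**What to change.** Before unblinding, amend SAP 9.3 and 9.9.3.5 to define a separate biomarker PPS that:
- omits the compliance and exposure criteria;
- keeps the baseline-eligibility, baseline-cognition, incorrect-stratum, wrong- or switched-treatment and premature-unblinding exclusions;
- counts only the retained criteria toward the 5% trigger for the biomarker per-protocol analysis.

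The trigger has to change with the set; otherwise adherence violations would still decide whether the analysis runs. Leave the efficacy PPS as it is. SAP 9.2 already allows its list to be revised before final unblinding. The cost is a short SAP edit and a second flag variable.

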7.2 Exclusion Criteria

Any subject who meets any of the following criteria will not qualify for entry into the study:

1. The subject has a current diagnosis or history of any type of cognitive impairment or dementia, or has a current diagnosis or history of neurological/psychiatric disorder or any other diagnosis that significantly affects cognitive performance (eg, mental retardation, organic mental disorder).
2. The subject has a current diagnosis of significant psychiatric illness, per Diagnostic & Statistical Manual of Mental Disorders, 4th Edition - Text Revision (DSM-IV-TR) (or

CONFIDENTIAL

- 35DSM-V when published) (including but not limited to major depressive disorder, anxiety disorders) and is in an acute phase/episode, or the subject has a current diagnosis or history of schizophrenia or bipolar disorder.
3. The subject has a glycosylated hemoglobin (HbA1c) >8.0% at the time of baseline or requires treatment with insulin, triple oral antidiabetic therapy or a PPAR- γ agonist. The subject should be on a stable antidiabetic regimen for at least 3 months prior to enrollment.
 4. The subject has a clinically significant unstable illness, for example, hepatic impairment or renal insufficiency, or cardiovascular, pulmonary, gastrointestinal (including s/p gastric bypass), endocrine, neurological, rheumatologic, immunologic, infectious, skin and subcutaneous tissue disorders, or metabolic disturbance. History of human immunodeficiency virus (HIV) infection is considered exclusionary for this study.
 5. The subject has a history of drug abuse (defined as any illicit drug use) or a history of alcohol abuse/dependence within 2 years prior to the Screening Visit.
 6. The subject is an immediate family member, testing center employee, or is in a dependent relationship with a testing center employee who is involved in conduct of this study (eg, spouse, parent, child, and sibling) or may consent under duress.
 7. The subject has a history of hypersensitivity or allergies to pioglitazone or related compounds.
 8. The subject is required to take excluded medications as specified in the Excluded Medications Section (Section 7.3).
 9. The subject had any of the following values at the Baseline Visit (Visit 2):
 - a) A serum total bilirubin value >1.5 \times upper limit of normal (ULN).
 - b) A serum alanine aminotransferase (ALT) or aspartate aminotransferase (AST) value >2 \times ULN.

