9.1.7 Documentation of Concurrent Medical Conditions

Concurrent medical conditions are those significant ongoing conditions or diseases that are present at signing of informed consent. This includes clinically significant laboratory, ECG, or physical examination abnormalities noted at baseline examination. The condition (ie, diagnosis) should be described.

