6. Subjects with T2DM who are on a stable antidiabetic regimen for at least 3 months prior to enrollment that does not require the use of insulin, oral triple therapy and/or PPAR- γ agonists will be allowed in the study. Subjects who develop a new onset T2DM during the study will be referred to an endocrinologist. If the use of prohibited medications (such as insulin or PPAR- γ agonists) is considered necessary, the subject will be withdrawn from the study. Pioglitazone alone especially at a low dose is not likely to cause hypoglycemia in elderly subjects without T2DM. However, subjects with T2DM taking pioglitazone with an insulin secretagogue (eg, sulfonylurea or glitinide) may be at increased risk for developing hypoglycemia. Therefore all subjects with the following AEs will be closely monitored using the following event categories [70].

- **Severe hypoglycemia:** an event requiring assistance of another person to actively administer carbohydrate, glucagon, or other resuscitative actions. Blood glucose may not be available.
- **Documented symptomatic hypoglycemia:** typical symptoms of hypoglycemia accompanied by blood glucose ≤ 70 mg/dL (3.9 mmol/L).
- **Asymptomatic hypoglycemia:** Blood glucose ≤ 70 mg/dL (3.9 mmol/L), but with no typical symptoms.
- **Probable symptomatic hypoglycemia:** Symptoms of hypoglycemia that are not accompanied by blood glucose determination ≤ 70 mg/dL (3.9 mmol/L).
- **Relative hypoglycemia:** Symptoms of hypoglycemia, but with a measured blood glucose > 70 mg/dL (3.9 mmol/L).

If any subject is noted to have a hypoglycemic event, the hypoglycemia (e)CRF should be completed within 24 hours of the investigator's awareness of the event.

All special interest AEs also have to be recorded as AEs in the (e)CRF.

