Composite scores will be derived from the test battery. Each test in the battery falls into one of the following cognitive domains: Episodic Memory (CVLT-II, BVMT-R), Executive Function (TMT Part B, Digit Span Backwards), Language (Animals, Lexical/Phonemic Fluency), Attention (Digit Span Forward, TMT Part A), and Visuospatial (CDT, BVMT-Copy). Only the domains of episodic memory, executive function, language, and attention will be used for the composite score (ie, CDT, BVMT-Copy and the MINT, which do not allow generation of standard z scores, will only be used for diagnostic purposes and will be excluded from the calculation of the composite score). To form the composite, z-scores will be calculated for each

CONFIDENTIAL

test, each z-score for the domain will be averaged, and then all relevant domains will be averaged to form the composite. Because there are two tests for each domain, the composite can still be calculated if one test is missing. In the case of memory however, both tests are required to calculate the composite.

There may still be missing values for the continuous variables and the analyses for continuous variables are based on a Missing at Random (MAR) assumption. As a sensible sensitivity analysis, the pattern mixture models using standard SAS STAT procedures will be performed. This method uses sequential regression and multiple imputation methodology to impute missing values after subjects' discontinuation from the study. The missing values from both control and experimental treatment arms are imputed based on the available data from control subjects and through using PROC MI's methodology for imputation of monotone missing data patterns to impute the outcome variables at consecutive visits in a sequential (chain) manner.

Additional analyses may be done to assess the contribution of age, APOE genotype, and TOMM40 rs10524523 genotype to the risk assignment algorithm.

It is anticipated that approximately 20% of the subjects will be diabetic. Subgroup analyses for non-diabetic subjects and for diabetic subjects will be done to support the results of the primary analysis.

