9.14.2 Clinical Laboratory Evaluations

The following clinical laboratory parameters will be summarized:

- Serum chemistry including alanine aminotransferase (ALT), alkaline phosphatase, aspartate aminotransferase (AST), total bilirubin, GGT, total protein, albumin, creatinine, blood urea nitrogen (BUN), potassium, sodium, glucose, calcium, vitamin B12, folate, parathyroid hormone (PTH), thyroid stimulating hormone (TSH), and free thyroxine (free T4). (Direct bilirubin will be assessed only if total bilirubin ≥ 2.0 mg/dL. Vitamin B12, folate, and RPR is

collected only at Baseline and as part of the comprehensive medical follow-up evaluation to rule out other causes of dementia).

- Hematology including red blood cells, white blood cells, neutrophils, eosinophils, basophils, lymphocytes, monocytes, hemoglobin, hematocrit, platelets, and HbA1c. (HbA1c is collected only at Baseline.)
- Urinalysis including pH, specific gravity, glucose, and nitrite. (Protein and blood values will not be summarized but will be included in the listings.)

For each laboratory parameter, the following will be displayed for each scheduled time point (each visit and end of study).

- Summary statistics (n, mean, SD, median, minimum, and maximum) by treatment group and overall for the actual values and change-from-Baseline values.
- Shift tables for the change from Baseline to each post-baseline time point will be presented. For these tables each subject will be categorized as low, normal, or high for the baseline value and low, normal, or high for each post-Baseline time point, according to the central laboratory reference ranges. The number of subjects in each of the combinations of shifts will be presented.
- Markedly abnormal values for laboratory parameters, as defined in [Appendix A](#), will be summarized by treatment group and overall. The number and percentage of subjects with MAV values observed post-Baseline in each of the applicable laboratory parameters will be presented.
- Number and percentage of subjects with elevated liver enzyme lab values will be presented using the criteria described in the protocol.

Subject mappings will be provided for markedly abnormal lab values and elevated liver enzyme lab values.

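### Diabetic status in the SAP subgroup analysis rests on baseline HbA1c alone, so treated diabetics below 6.5% are analysed as non-diabetic

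*SAP*

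**What the plan says.** SAP 9.9.3.5 lists the subgroups for the primary efficacy and primary biomarker comparisons. One of them is "baseline diabetic status (non-diabetic: baseline HbA1c <6.5%, diabetic: baseline HbA1c" at or above 6.5%). No other criterion enters the rule. SAP 9.14.2 notes that "HbA1c is collected only at Baseline", so a single value fixes each subject's label. SAP 9.5 lists diabetic status among the baseline characteristics without defining it.

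The protocol treats diabetes as a condition with a regimen. Section 10.2.1.3 allows into the study "Subjects with T2DM who are on a stable antidiabetic regimen for at least 3 months prior to enrollment", provided the regimen does not need insulin, triple oral therapy or a PPAR-γ agonist. Section 7.2 excludes a subject with "glycosylated hemoglobin (HbA1c) >8.0% at the time of baseline or requires treatment with insulin" or the other listed treatments. It sets a ceiling on HbA1c but no floor.

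On analysis, Protocol 13.1.3 says "It is anticipated that approximately 20% of the subjects will be diabetic" and commits that "Subgroup analyses for non-diabetic subjects and for diabetic subjects will be done to support the results of the primary analysis". It gives no HbA1c definition. SAP 9.17, which records changes from the protocol's analysis plan, does not mention the HbA1c rule.

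**The concern.** In a treated subject, HbA1c reflects the treatment as well as the disease. The protocol deliberately admits treated diabetics, so a rule that looks only at HbA1c sends those with good control to the wrong side of the split. A subject with diagnosed diabetes on a stable regimen and an HbA1c of 6.3% would be counted as non-diabetic.

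This has two consequences. The estimate labelled non-diabetic describes a mixed population. The estimate labelled diabetic describes only diabetics with HbA1c from 6.5% to 8.0% (protocol violators apart), and it rests on fewer subjects and events than the protocol's expected share implies. Any real difference in effect between diabetics and non-diabetics would be blurred.

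The question is of some interest because pioglitazone is an approved treatment for type 2 diabetes (Protocol 4.1) and insulin sensitivity is among the pathways that Protocol 4.2.2 mentions. If SAP 9.5 uses the same rule, the baseline table will also under-count diabetics.

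**Working it through.** **The plan's own figure.** The subgroup has no power statement of its own, so the figure to reproduce is the 202 events in Protocol 13.3. Five-year event rates of 15% and 9% under an exponential model give HR = ln(0.91)/ln(0.85) = 0.580. Schoenfeld's formula, with two-sided alpha 0.01, 90% power and 1:1 allocation, gives 4 × (2.576 + 1.282)² / (ln 0.580)² = 201 events. This agrees with the stated 202, and nothing in it depends on the subgroup rule.

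**Inputs for the misclassification.**
- Share of diabetics: 20% (Protocol 13.1.3), taken to apply to the primary efficacy population.
- High-risk sample: 2,346 subjects and 202 events (Protocol 13.3).
- f, the share of diabetics with baseline HbA1c below 6.5%: not in the documents. Assumed range 10% to 70%.
- Event rates: assumed equal in diabetics and non-diabetics.

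**Formulas.**
- Diabetics labelled non-diabetic, as a share of all subjects: 0.20f.
- Diabetic fraction of the labelled non-diabetic group: w = 0.20f / (0.80 + 0.20f).
- Labelled diabetic share: 0.20(1 − f).
- Events in the labelled diabetic group: 202 × 0.20(1 − f).

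| f | Subjects moved | w | Labelled diabetic share | Subjects | Events |
|---|---|---|---|---|---|
| 0 (reference) | 0 | 0% | 20% | 469 | 40 |
| 10% | 47 | 2.4% | 18% | 422 | 36 |
| 30% | 141 | 7.0% | 14% | 328 | 28 |
| 50% | 235 | 11.1% | 10% | 235 | 20 |
| 70% | 328 | 14.9% | 6% | 141 | 12 |

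**Effect on the non-diabetic estimate.** Take an extreme case: HR 0.580 in non-diabetics and 1.0 in diabetics, with the same placebo rate. The apparent HR in the labelled non-diabetic group is then approximately (1 − w) × 0.580 + w × 1.0. For f = 10%, 30%, 50% and 70% this gives 0.59, 0.61, 0.63 and 0.64.

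**Effect on the diabetic estimate.** For HR 0.58 at two-sided 0.05, power with about 40 events is about 41%. It falls to about 37%, 30%, 23% and 16% over the same values of f.

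**Undiagnosed subjects.** If the 20% counts diagnosed cases only, and a further share u of subjects is undiagnosed with HbA1c of at least 6.5%, the labelled diabetic share becomes 0.20(1 − f) + u. A definition that adds diagnosis and medication gives 0.20 + u. So u offsets the shrinkage, but the share placed differently by the two rules is still 0.20f. The documents give no value for u.

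**The case against.** The strongest reply is that this is a labelling matter in a supportive analysis, with a small effect. Much of that stands. Diabetic status is one of eight listed subgroups, outside the testing hierarchy in SAP 9.9.8. HbA1c is measured before dosing and the rule is the same in both arms, so the randomised comparison within each labelled subgroup is valid. Even in the extreme case above, the non-diabetic HR moves only from 0.58 to at most 0.64. The diabetic subgroup is weak under either definition, and the SAP already warns that "Analysis results for subgroups containing less than 20% of the total subjects in the primary efficacy analysis population should be interpreted especially cautiously". SAP 9.9.3.5 also allows further subgroup variables if necessary, and text after the list is blacked out, so other planned analyses cannot be ruled out. None of this corrects the written rule.

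The documents do not support four stronger readings that a reader might infer:
- **That both subgroups are contaminated.** The rule moves diabetics into the non-diabetic group, but puts no non-diabetics among those at or above 6.5%. The diabetic group is depleted and selected, which is a different fault.
- **That the diabetic group keeps only poorly controlled cases.** Entry is capped at HbA1c 8.0% without insulin or triple oral therapy, and SAP Appendix A flags HbA1c as markedly abnormal only above 7%. The accurate description is HbA1c 6.5-8.0%.
- **That this is the trial's main subgroup question.** Protocol 13.1.3 gives it a supporting role, and Protocol 6.3.2 rests the dose rationale on a mitochondrial effect at doses well below those used for diabetes.
- **That the misplaced share is known.** Any value of f is an assumption, and Protocol 13.1.3 does not say how its 20% was defined.

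**Conclusion.** The point holds as a definitional error. Applied as written, SAP 9.9.3.5 classes treated diabetics with HbA1c below 6.5% as non-diabetic. This does not match the protocol's concept of diabetes, and no visible text corrects it.

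The size is conditional. With 20% diabetics, equal event rates and f between 10% and 70%, about 2-15% of the labelled non-diabetic group would be diabetic. The labelled diabetic group would fall from about 20% to 18-6% of subjects, and from about 40 to 36-12 events, before any offset from undiagnosed subjects. Without that offset, it falls below the SAP's own 20% caution line for any f above zero.

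The main harm is a mislabelled non-diabetic population and a smaller, unrepresentative diabetic one. Bias in the non-diabetic hazard ratio is modest. The primary analysis, alpha, event target and sample size are unaffected. This is a minor correction.

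**What to change.** Before unblinding, amend SAP 9.9.3.5 to define a subject as diabetic if any of these holds: a recorded diabetes diagnosis in medical history or concurrent conditions, antidiabetic medication at baseline, or baseline HbA1c of at least 6.5%. Define non-diabetic as none of these. Use the same definition for diabetic status in SAP 9.5, and keep the HbA1c-only split as a sensitivity analysis.

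The data are already collected. Protocol 9.1.7 provides for recording the diagnoses: "Concurrent medical conditions are those significant ongoing conditions or diseases that are present at signing of informed consent". These are MedDRA-coded under SAP 9.6, and medications are WHO Drug-coded under SAP 9.7. SAP 9.9.3.5 already derives statin use from drug groupings, so a medication-based subgroup needs no new method.

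The cost is a few lines of SAP text, one derived variable and one extra subgroup table. The timing matters: after unblinding, the same change would look driven by the data.
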